5.5 Data Collection

Eligible subjects will be treated with the Pipeline™ Flex Embolization Device with Shield Technology™.

Subjects will undergo standard of care follow-up visits. Data generated per standard of care will be collected for 1 year (± 8 weeks) beyond the index procedure. All follow-up visits and telephone calls during this time period will be recorded. A summary of the data to be collected is listed in **Table 5-1**.

In order to track compliance with antiplatelet therapy, subjects will be contacted at a minimum of approximately (± 14 days), 3 (± 30 days), 6 (± 6 weeks), and 12 (± 8 weeks) months post-index procedure and asked to confirm their current antiplatelet regimen and that all relevant adverse events (**Section 6**) have been reported.

A survey will be administered to all centers to collect their standard antiplatelet therapy regimen at the start of the study and annually.

Table 5-1. Data Collection

Time Period	Data to be Collected
Baseline	
• Relevant medical history and demographics• Aneurysm characteristics, symptoms and status (ruptured or unruptured)• Hunt & Hess Grade and WFNS (if ruptured)• Antiplatelet medication use within past 30 days• Other relevant concomitant medications• Platelet reactivity testing• NIH Stroke Scale (NIHSS)• Modified Rankin Scale (mRS)
Procedure	
• Relevant medications including antiplatelet regimen• Adverse events• Platelet reactivity testing• Procedure and fluoroscopy times• Study device information including side branches covered• Concomitant treatments• Deployment success at target IA• Imaging to be sent to the Core Lab*• Aneurysm occlusion• NIHSS• mRS
Post-Implant Follow-up	
• Relevant medications including antiplatelet regimen• Adverse events• Platelet reactivity testing• Imaging to be sent to the Core Lab*• Aneurysm occlusion• Retreatment• NIHSS• mRS

*All imaging taken (e.g., angiograms, CT, MR, rotational angiography with 3D reconstruction, cone-beam CT, etc.) should be provided to the Core Lab.

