5.8 Study Exit

The subject will be seen by the treating physician according to standard care following intracranial aneurysm treatment. One year post-procedure, the subject will exit the study and be exempt from further data collection.

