mRS	Modified Rankin Score	Scale for measuring general neurological function. 0 No symptoms at all 1 No significant disability despite symptoms; able to carry out all usual duties and activities 2 Slight disability; unable to carry out all previous activities, but able to look after own affairs without assistance 3 Moderate disability; requiring some help, but able to walk without assistance 4 Moderately severe disability; unable to walk without assistance and unable to attend to own bodily needs without assistance 5 Severe disability; bedridden, incontinent and requiring constant nursing care and attention 6 Dead
NIHSS	National Institute of Health Stroke Scale	Method for quantifying neurologic deficits developed by the National Institutes of Health. It is used to assess the severity of a stroke.
PED	Pipeline Endovascular Device	Pipeline Endovascular Device

Abbreviation	Abbreviated Term	Definition
Primary Efficacy Endpoint	Complete aneurysm occlusion (defined as Raymond-Roy grade 1 ⁵⁵) without significant parent artery stenosis (\leq 50%) or retreatment of the target aneurysm 1-year post-procedure	The primary effectiveness endpoint assessed by: 
• Occlusion status: by a 3-member adjudicated read by the imaging Core Laboratory according to the Scale of Roy• Parent Artery stenosis: by the 3-member adjudicated read by the imaging Core Laboratory.• Retreatment: by the investigator reported events of retreatment.

Abbreviation	Abbreviated Term	Definition

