times as many subjects, the small sites will be ranked by size and divided into 2 pooled assignments using an alternating sequence (ABABAB). If the pooled smaller sites represent a site that has more than three times as many subjects as the largest single site, however less than 4 times as many subjects, the small sites will be ranked by size and divided into 3 pooled assignments using an alternating sequence (ABCABCABC).

Imputation of Outcome Data

Missing data for subjects who fail to complete study follow-up without any evidence of a major stroke in the territory supplied by the treated artery or neurological death will be imputed in the analysis of primary safety using the multiple imputation procedure from SAS (Proc MI). Subjects who withdraw from the study prior to completion and have experienced a major stroke in the territory supplied by the treated artery or neurological death at any time will be counted as having experienced the event of interest. A separate tabulation will be provided based on the observed data: subjects who withdraw from the study prior to completion without any evidence of a major stroke in the territory supplied by the treated artery or neurological death will be counted as not having experienced the event of interest. For effectiveness, since follow-up imaging of the target aneurysm was not required at each study visit but was instead performed according to standard of care, the primary endpoint will be assessed using a selection rule, according to the following preferences:

- Imaging from day 141 (the opening of the 6-month follow-up window) onward is eligible to be included; imaging earlier than day 141 is disregarded for this analysis but imaging after the end of the 1 year window is still eligible.
- We will use the last adjudicated image at any time starting from day 141, UNLESS
- - o The last image is a CTA and there is a DSA within 90 days prior to the CTA, in which case the DSA will be used, OR
 - o The last image is an MRA and there is a DSA or CTA within 90 days prior to the MRA, in which case the DSA or CTA will be used. For this sub-rule we will prefer DSA over CTA if both exist.

The rules above define the available data for the purpose of endpoint calculations and effectiveness tables and listings. For subjects with no qualifying imaging per the above preference rules, multiple imputation will be employed to handle missing data for primary effectiveness.

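### The image rule for the 1-year effectiveness endpoint has no closing day, so an image taken after the 1-year window displaces a valid image from inside it

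*SAP*

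**What the plan says.** The SAP defines the primary effectiveness endpoint at 1 year (sections 2, 5 and 7.9). Success needs Raymond-Roy grade 1 closure, parent-artery narrowing of no more than 50%, and no second treatment of the target aneurysm. Section 6 sets the 50% threshold against the 1-year incidence.

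SAP 7.4 says which image is scored:

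- Lower limit: "Imaging from day 141 (the opening of the 6-month follow-up window) onward is eligible to be included".
- Upper limit: none, because "imaging after the end of the 1 year window is still eligible".
- Choice: "We will use the last adjudicated image at any time starting from day 141, UNLESS" a better modality exists within the 90 days before a final CTA or MRA.

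The reason given is that imaging followed standard of care and was not required at every visit.

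On the period of observation, Protocol 5.5 says that standard-of-care data "will be collected for 1 year (± 8 weeks) beyond the index procedure". Protocol 5.8 says that at one year "the subject will exit the study and be exempt from further data collection". Protocol 3.1 and 9.4 list occlusion at 1 year and occlusion at last follow-up as separate outcomes.

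On retreatment, SAP section 2 says that component is assessed "by the investigator reported events of retreatment". SAP 7.13.3 instead describes retreatment as adjudicated by the imaging core laboratory.

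**The concern.** The stated reason supports a late image as a fallback for a subject who has no image near 1 year. It does not support setting aside an image that was taken at 1 year. The rule does both, so a rate labelled 1-year becomes a last-available-image rate for anyone scanned again later.

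The retreatment component raises a second problem. It is tied to the same time point ("or retreatment of the target aneurysm 1-year post-procedure"), and no passage provides for reporting retreatment after exit. If a late image is used, a retreatment between exit and that image might not be known. Even if it were known, the wording does not clearly make it a failure.

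What is at stake is comparability. SAP section 3 intends to contrast the results with Pipeline studies of the uncoated device and to support a US indication evaluation. A rate that mixes in images of any later date is not comparable with a true 1-year rate.

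**Working it through.** **1. Window arithmetic.** The SAP's schedule of assessments gives ±6 weeks at 6 months and ±8 weeks at 1 year.

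- Opening of the 6-month window: 183 − 42 = day 141, which reproduces the SAP's figure. Counting 6 months as 180 days would give day 138.
- 1-year window: 365 ± 56 = days 309 to 421. The selection rule contains no counterpart to day 421.

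**2. The rule applied to one subject.** Take a DSA on day 365 and an MRA on day 500. The gap is 500 − 365 = 135 days, more than 90, so the modality exception does not apply. The MRA is scored and the 1-year DSA is discarded.

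**3. Do other planned analyses correct this?** SAP 7.9 plans a worst-case and a tipping-point analysis for missing data. A subject with a late image counts as observed, so neither reaches the problem. SAP 7.7 plans summaries by visit, but SAP 7.4 applies its selection rule to effectiveness tables generally. Nothing in the visible text limits the primary endpoint to images inside the window.

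**4. Direction.** Protocol 1.2.3 reports complete occlusion in an earlier Pipeline trial in large and giant aneurysms:

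- 1 year: 79/91 = 86.8% (exact 95% CI 78.1 to 93.0), so 13.2% not closed.
- 5 years: 59/62 = 95.2% (86.5 to 99.0), so 4.8% not closed.

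The denominators differ, the intervals overlap and the time points are four years apart. The figures suggest that occlusion rises with time; they do not measure the change a few months past day 421.

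**5. Size.** Let f be the share of subjects whose scored image is post-window, p the true 1-year success rate, and c the share of 1-year failures that read as success on the late image. Then

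shift = f × (1 − p) × c

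The documents give none of these for this study; all are assumptions. The formula counts only changes from failure to success.

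| 1 − p | f | c | Shift (points) |
|---|---|---|---|
| 13.2% (earlier trial) | 10% | 10% | 0.13 |
| 13.2% (earlier trial) | 30% | 60% | 2.4 |
| 30% (p = 70%) | 5% | 10% | 0.15 |
| 30% (p = 70%) | 10% | 25% | 0.75 |
| 30% (p = 70%) | 20% | 50% | 3.0 |
| 30% (p = 70%) | 30% | 50% | 4.5 |

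**6. Effect on the reading.** With N = 200 and the exact two-sided 95% interval of SAP section 6:

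- 140/200 = 70.0% (63.1 to 76.3)
- 145/200 = 72.5% (65.8 to 78.6)
- 150/200 = 75.0% (68.4 to 80.8)

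All three clear 50%. The lower bound first exceeds 50% at 115/200 (57.5%). The threshold reading is sensitive only when the true rate is close to 50%. At exactly 50%, the chance of reaching 115 successes is 2.0% with no shift, 3.8% with +1 point, 8.9% with +2.5 points and 26.2% with +5 points.

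**The case against.** A reader might infer that an aneurysm still open at 1 year, retreated after exit and then seen closed is bound to score as a success. The documents do not establish this. Protocol 5.5 and 5.8 end all data collection, images as well as retreatment, so a post-window image may simply come from a subject whose last visit ran late and who has not yet exited. The SAP's schedule gives follow-up imaging and retreatment the same code at the same visits. SAP 7.13.3 assigns retreatment to the core laboratory, which might recognise it on the image. What stands is that no passage provides for capturing retreatment after exit, and that the two statements of its source conflict.

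A reader might also infer that the reported rate is inflated overall. That too goes further than the text allows. A late image can show recurrence or stenosis above 50% and turn a success into a failure. At its other end, the same rule accepts images from day 141, which would pull the rate down if occlusion rises with time.

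A hard cap at day 421 would also have a cost. A subject imaged on days 150 and 425 would be scored on day 150, which is 215 days from 1 year instead of 60. A subject imaged only on day 425 would go to multiple imputation despite having a core-laboratory reading. This objection stands, and the fix below keeps such images.

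Finally, there is no formal success criterion (Protocol 9.2; SAP 7.13.1), and the additional effectiveness analyses in SAP section 5 are redacted, so an in-window analysis may exist there. Neither justifies replacing a 1-year image in an endpoint labelled 1-year.

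**Conclusion.** The point holds in this form: an image from after the 1-year window replaces a valid image from inside it, in an endpoint and a threshold comparison both defined at 1 year. Two outcomes that the protocol keeps apart are thereby merged. This follows directly from the text.

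The loss of retreatment information is a possibility inferred from the end of data collection and the investigator-reported source. It is not an established consequence. An upward bias is the likelier direction, on unpaired data from one earlier trial. The size is unknown because the number of post-window images is not given; the 0.1 to 4.5 points above rest wholly on assumed f, p and c. For comparison, the interval at 140/200 is about ±6.6 points wide. At true rates near 70% the reading against 50% would probably stay the same. The change is worth making because the estimate itself, and any contrast with other Pipeline studies, should match its 1-year label.

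**What to change.** In SAP 7.4:

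1. When an adjudicated image exists in the 1-year window (days 309 to 421), state that a later image may not replace it in the primary endpoint.
2. Use a post-window image only when no image in the 1-year window exists, and report how many subjects are scored this way.
3. Count any retreatment up to the date of the selected image as failure, in addition to retreatment within the 1-year period that the endpoint already covers.
4. Add a sensitivity analysis that uses only images up to day 421.
5. Report other late images under last follow-up, as the protocol's outcome list already allows.
6. Reconcile the source of retreatment between SAP section 2 (investigator) and SAP 7.13.3 (core laboratory).

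The cost is a few sentences and a little more analysis work. The rate may come out slightly less favourable.

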21 DEFINITIONS

TERM	DEFINITION
Adverse Event (AE)	
Any untoward medical occurrence, unintended disease or injury, or untoward clinical signs (including abnormal laboratory findings) in subjects, users or other persons, whether or not related to the investigational medical device. (ISO 14155:2011 3.2)
 
Note 1: This definition includes events related to the investigational medical device or the comparator.
 
Note 2: This definition includes events related to the procedures involved.
 
Note 3: For users or other persons, this definition is restricted to events related to investigational medical devices.

Adverse Device Effect (ADE)	
An adverse event related to the use of an investigational medical device. (ISO 14155:2011 3.1)
 
Note 1: This definition includes adverse events resulting from insufficient or inadequate instructions for use, deployment, implantation, installation, or operation, or any malfunction of the investigational medical device.
 
Note 2: This definition includes any event resulting from use error or from intentional misuse of the investigational medical device.

Device Migration	
Movement of one or more Pipeline™ Flex Embolization Device with Shield Technology™ of more than 5 mm in its parent artery location in comparison to the post-placement angiogram.

Device-related Adverse Effect	
Event has a strong temporal relationship to the study device, and alternative etiology is less likely.

TERM	DEFINITION
Procedure	The primary study procedure involving the placement of the Pipeline™ Flex Embolization Device with Shield Technology™ at Day 0.
Neurological Adverse Event	An adverse event with an underlying neurological cause.
Neurological Death	Subject death due to neurologic reasons.
Point of Enrollment	Once the subject has signed and dated the Informed Consent or DRF, point at which the Pipeline™ Flex Embolization Device with Shield Technology™ is advanced into the micro catheter inside the subject.
Procedure-related Adverse Event	Event has a strong temporal relationship to the procedure (Day 0). This includes AEs attributable to any device(s) other than the Pipeline™ device used at procedure (Day 0), such as access devices, delivery microcatheters, non-ionic contrast, guidewires, or any other adjunctive, approved/cleared device for treatment of intracranial aneurysms.
Retreatment	Any subsequent intervention (post study procedure with Pipeline implant) performed to treat the target IA.

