ICH	International Conference for Harmonization	An Organization whose main purpose is to achieve greater harmonization to ensure that safe, effective, and high-quality medicines are developed and registered in the most resource-efficient manner.
IDE	Investigational Device Exemption	An approved IDE permits a device that would otherwise be required to comply with a performance standard or would require a premarket approval to be shipped lawfully for the purpose of conducting investigations of that device (21 CFR 812).
I/E	Inclusion/Exclusion Criteria	A list of conditions that would include or exclude a patient from enrolling/participating in a clinical study as outlined in the study protocol.
Implant Failure	Implant Failure	Enrolled subjects who underwent the study procedure and in whom an attempt to implant the device was made but was unsuccessful

Abbreviation	Abbreviated Term	Definition
IRB	Institutional Review Board	Any board, committee, or other group formally designated by an institution to review biomedical research involving subjects and established, operated and functioning in conformance with 21 CFR 56.
ITT	Intent-to-Treat	The Intention to Treat (ITT) population includes all enrolled subjects in whom deployment of the Pipeline™ device with Shield Technology™ was attempted. It is possible that the Pipeline™ device with Shield Technology™ may not reach the target site and the operator would not attempt to deploy it, in the rare event that happens, that patient will not be considered part of the ITT population.
MedDRA	Medical Dictionary for Regulatory Activities	Standardized medical terminology developed by ICH to facilitate sharing of regulatory information internationally for medical products used by humans. It is used for registration, documentation and safety monitoring of medical products both before and after a product has been authorized for sale. Products covered by the scope of MedDRA include pharmaceuticals, vaccines and drug-device combination products.

Abbreviation	Abbreviated Term	Definition

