Subjects will be considered enrolled in the study once the patient has signed and dated the Informed Consent or DRF and the Pipeline™ Flex Embolization Device with Shield Technology™ is advanced into the micro catheter inside the patient. Per each site’s standard of care procedure, at screening, each patient can undergo a neurologic examination and assessment using the mRS and NIHSS, blood draw for hematocrit, platelet count, platelet function testing, serum creatinine, and a pregnancy test (if applicable). Pertinent medications taken by the study participant starting on the day of study procedure were collected while for platelet reactivity start date can also be > 30 days before procedure (in case patient was already under antiplatelet, including anticoagulants and antiplatelet therapy). Subjects will be assessed and documented at baseline. Patient eligibility assessment is to be performed based on data available to the investigator at the time of screening. Patient will be considered a screen failure if:

- The patient signs the informed consent or DRF but fails to meet study inclusion/exclusion criteria during the screening and baseline phase.
- The patient signs the informed consent or DRF, meets the study inclusion/exclusion criteria but an attempt to implant the Pipeline™ Flex Embolization Device with Shield Technology™ is not performed.

The investigator will assess device occlusion, device placement and overall status of the aneurysm. At the investigator’s discretion, the target IA may be retreated at any time during the study. In such situations, the date of the initial procedure (and not the date of the retreatment) will be considered Day 0.

If the target IA undergoes an attempted deployment with the Pipeline™ device with Shield Technology™ but is not implanted or receives an alternate treatment (e.g., coils), the patient is considered an implant failure and will be followed up until hospital discharge. However, if the target IA does not undergo an attempted deployment with the Pipeline™ device with Shield Technology™ and is not treated or receives an alternate treatment (e.g., coils) during the initial procedure, the patient is considered a screen failure and no further follow up is required.

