The patient will be tested at the discretion of the site per standard of care procedures for antiplatelet response and the appropriate dose of antiplatelet agents will be given after the Pipeline™ device with Shield Technology™ placement procedure. Medications could be continued as medically indicated.

Estimated Duration of Patient Participation

Up to 200 subjects will be enrolled over a period of approximately 24 months. The study is intended to have 200 subjects undergo attempted deployment of the Pipeline™ device with Shield Technology™. Each study patient will be followed for 1 year after the primary study procedure. Study participation includes consent, initial screening and baseline, treatment using the Pipeline™ device with Shield Technology™, discharge exam and follow-up visits at approximately 30, 90, 180 days, and 1 year. The total study duration is expected to be approximately 3 years.

Schedule of Assessments

	Baseline	Procedure	Discharge	1 Month	3 Months	6 Months	1 Year	Unscheduled
Schedule		Day 0		±14 days	±30 days	±6 weeks	±8 weeks	
Eligibility	X							
Demographics	X							
Aneurysm Symptoms	X	O	O	O	O	O	O	OR
Medical History		X						
Study Procedure		X						
Procedure Imaging		XR						
Ancillary Devices		X						
Study Device		XR						
Discharge			X					
Follow Up				X	X	X	X	XR
Follow-Up Imaging				OR	OR	OR	OR	OR
NIHSS	O	X		O	O	O	O	OR
mRS	O	X		O	O	O	O	OR
Exit			X					

Retreatment Study Procedure				OR	OR	OR	OR	OR
Labs	OR	OR	O	O	O	O	O	OR
Device Specific Event		OR	OR	OR	OR	OR	OR	OR
Adverse Event Assessment		OR	OR	OR	OR	OR	OR	OR

Key: Required=X Optional=O Repeatable=R

ANALYSIS POPULATIONS

The following populations will be considered for the analysis of data for this study:

Intent to Treat (ITT)

The Intention to Treat (ITT) population includes all consented subjects in whom deployment of the Pipeline™ device with Shield Technology™ was attempted.

Full Analysis Set (FAS)

The Full Analysis Set (FAS) population is a subset of the ITT population including only those subjects in whom the Pipeline™ device with Shield Technology™ was implanted.

Internal Carotid Artery (ICA) Population

The Intra-Cranial Artery Population (ICA) is a subset of the ITT population including only those subjects in whom the Pipeline™ device with Shield Technology™ was implanted in the ICA (segments C2-C7).

Non-ICA Population

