7.2.2 General Conventions for Summarization

Summary statistics will consist of the number and percentage of responses or counts at each level for categorical variables (e.g. gender). For continuous variables, the sample size (n), mean, median, standard deviation (SD), minimum, and maximum values will be presented.

All mean and median values will be formatted to one more decimal place than the measured value. Standard deviation values will be formatted to two more decimal places than the measured value. Minimum and maximum values will be presented with the same number of decimal places as the measured value.

The number and percentage of responses will be presented in the form XX (XX.X%).

- All summary tables will include the analysis population sample size (i.e., number of subjects).
- Relative Study Day 0 is defined as the day the patient underwent the study procedure. All study days are determined relative to the day the patient underwent the study procedure.
- Baseline values will be defined as those values recorded immediately prior to the study procedure.
- Change from baseline for differences will be calculated as follows:

$$\text{Change} = \text{Post-baseline value} - \text{baseline value}$$

- Missing data may have an impact upon the interpretation of the trial data. The primary presentation of the overall primary endpoint results will be based on the observed data with multiple imputation for missing data using SAS PROC MI. A methodology is also defined in this section for addressing missing dates.
- Date variables will be formatted as DDMMYYYY for presentation; SAS Date9. format.

Data from this study, when applicable will be presented in a listing format. All listings will be sorted by patient number and date, as applicable.

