The incidence of complete aneurysm occlusion without significant parent artery stenosis ($\leq 50\%$) at 1 year post-procedure and without re-treatment of the target aneurysm (Primary Efficacy Endpoint) will be based on the Scale of Roy. Results will be based on the ITT population and will include the target aneurysm for each patient. The target aneurysm is defined as the largest aneurysm treated in the study procedure as identified by the core laboratory.

Results based on the ITT population will be presented in a table entitled *Overall Summary of the Post-Procedure Variables by Time*. The table will contain the point estimate and the confidence limit based on the exact Clopper-Pearson method. The supportive data for this table will be presented in a listing entitled *Post-Procedure Variables*. This listing will be sorted by patient number. Results based on the ICA population will be presented in a similar table and results based on the FAS population will be presented in a similar table.

Concomitant Medications

Concomitant medications refer to all medications taken from Day 0 thru study exit. *Antiplatelet medications were collected per their actual start date even if these were started prior to the study treatment (Day 0)*. *Prior medications* refer to all medications that were started and stopped prior to the first treatment with the Pipeline™ device with Shield Technology™ and will not be reported as concomitant.

The count and percent of subjects on anti-platelet medications will be summarized for 7 days pre-procedure, as well as for post procedure (were available) and presented in tables entitled *Summary of Dual Antiplatelet Therapy (DAPT)*. A summary of the concomitant medications will be presented in a table entitled *Summary of Concomitant Medications*, containing a clear declaration regarding the start date of the medication relative to the study procedure. The concomitant medications taken by the ITT population will be displayed in a listing entitled *Concomitant Medications*.

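### SAP 7.4 multiply imputes primary effectiveness for implant failures, who are in ITT but leave follow-up at discharge, and it does not settle how retreated subjects without a later image are scored

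*SAP*

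**What the plan says.** **Population.** SAP 7.7 says of the primary efficacy endpoint: "Results will be based on the ITT population and will include the target aneurysm for each patient". ITT needs only an attempted deployment (SAP 5 and 7.1.3). SAP 5 adds: "The Full Analysis Set (FAS) population is a subset of the ITT population including only those subjects in whom" the device was implanted. SAP 2 defines implant failures as "Enrolled subjects who underwent the study procedure and in whom an attempt to implant the device was made but was unsuccessful". They are therefore in ITT and not in FAS.

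**Follow-up.** Under SAP 5 (Study Procedure), if deployment is attempted but the device "is not implanted or receives an alternate treatment (e.g., coils), the patient is considered an implant failure and will be followed up until hospital discharge". Protocol 6 also ends follow-up at discharge for these subjects.

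**Missing outcomes.** SAP 7.4 accepts images from day 141 onward. It continues: "For subjects with no qualifying imaging per the above preference rules, multiple imputation will be employed to handle missing data for primary effectiveness". SAP 7.2.2 makes this the main presentation: the "primary endpoint results will be based on the observed data with multiple imputation for missing data using SAS PROC MI". SAP 7.4 also ties primary effectiveness, without exception, to the core laboratory's reading of images received.

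**Retreatment.** Absence of retreatment is part of the endpoint (SAP 2, 5 and 7.9). SAP 2 names the source: "Retreatment: by the investigator reported events of retreatment". SAP 7.13.3 instead has the imaging core laboratory adjudicate it. Protocol 21 defines retreatment as "Any subsequent intervention (post study procedure with Pipeline implant) performed to treat the target IA". SAP 7.2.1 defines a re-treatment procedure as treatment after the primary study procedure and does not require an implant.

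**The concern.** An implant failure has no late image because the plan ends that subject's follow-up at discharge, not because of ordinary dropout. The imputation rule treats the two cases alike. An imputation model fitted almost entirely to implanted subjects would then assign likely successes to subjects who do not carry the device. Making ITT primary should keep failed implantations in the result; this rule largely removes their effect.

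SAP 7.4 already uses a different principle for primary safety: a subject who withdraws after a known event is counted as having had it. Effectiveness has no parallel sentence. SAP 3 says the results will be contrasted with earlier Pipeline studies and used for a US indication evaluation, so a favourable tilt in the headline rate matters even without a formal test.

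**Working it through.** The plan gives no calculation to reproduce. SAP 6 reports no formal estimates, and Protocol 9.2 sets no success criteria.

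**Inputs**
- N = 200, the maximum enrolment (SAP 3).
- p = 75% success in the other subjects: assumed. Protocol 1.2.3 reports 75% complete occlusion (77/103) in the earlier prospective registry and 73.6% (78/106) complete occlusion without major stenosis at 180 days in the earlier single-arm trial.
- f = 2, 4 or 6 implant failures (1 to 3% of 200): assumed. The documents give no per-subject rate.
- q = success among implant failures under alternate treatment. q = 0 gives the upper bound. q = 40% is illustrative, taken from the low occlusion figure in Protocol 1.2.2 for coiling with balloons or stents in large, complex aneurysms.
- Imputation without covariates, because the visible text specifies no model.

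**Size.** Imputation gives implant failures an expected rate of p. The excess is (p − q) × f / N.

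| f | q = 0 | q = 40% |
|---|---|---|
| 2 | 0.75 × 2/200 = 0.75 points | 0.35 × 2/200 = 0.35 points |
| 4 | 1.50 points | 0.70 points |
| 6 | 2.25 points | 1.05 points |

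**How the planned presentations compare.** Take f = 4 and 20 other missing images (also assumed). Then 176 subjects have images, with 0.75 × 176 = 132 successes.
- Rule as written: (132 + 0.75 × 24)/200 = 150/200 = 75.0%.
- Implant failures scored as failures, the other 20 imputed: (132 + 15)/200 = 73.5%.
- FAS, the 20 imputed: 147/196 = 75.0%.
- Observed denominators, as illustrated in SAP 7.9: 132/176 = 75.0%.
- Worst case: 132/200 = 66.0%.

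The rule as written matches FAS. Worst case overshoots because it also fails all 20 ordinary missing images.

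**Against the 50% threshold (SAP 6).** The exact 95% lower limit is 68.4% at 150/200, so the reading is unaffected near 75%. At N = 200 the limit first exceeds 50% at 115 successes (57.5%; lower limit 50.33%, against 49.83% at 114). Only a reported rate just above that point could change sides. This ignores between-imputation variance, so I do not give an exact range.

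**Retreated subjects without a later image.** Two readings are open:
- SAP 2 makes an investigator-reported retreatment a failure of the composite, known without an image.
- SAP 7.4 imputes whenever imaging is absent and ties effectiveness to core laboratory readings, and SAP 7.13.3 gives retreatment itself to the core laboratory.

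If the second reading were followed, each such subject would add up to 0.75/200 = 0.375 points.

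**The case against.** **The endpoint does not require implantation.** It asks for an occluded target aneurysm without significant stenosis or retreatment. An aneurysm coiled after a failed implantation may be occluded, and scoring it as a failure would understate occlusion. This stands as a point about the estimand: failure scoring is a choice, and the documents do not dictate it. It does not support the present rule, which fills in these outcomes from subjects treated differently. The upward shift is therefore claimed only for the rate read as device success.

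**Sensitivity is already planned.** SAP 7.9 lists a worst-case analysis and an ITT tipping-point analysis. SAP 7.4 tabulates implant failures by reason, and SAP 7.7 reports implantation, so a reader can see how many there are. Part of the additional effectiveness list in SAP 5 is redacted. This limits the harm. But the visible analyses do not change the primary estimate, and the conventions in SAP 7.4 and 7.9 that drop missing subjects from the denominator do not score implant failures either.

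**The imputation model is open.** With implantation or retreatment as a predictor, the excess could be smaller. That is correct, and the figures above are illustrative.

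**A reader might infer that retreated subjects will certainly be imputed.** The documents do not support that. Under SAP 2 a reported retreatment settles the composite, and a settled outcome is arguably not missing. What holds is a conflict between sections. The protocol's wording on retreatment is not decisive for implant failures either: coiling at the index procedure also falls outside the SAP 7.2.1 definition, because it is not later treatment.

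**Conclusion.** The point holds for implant failures. SAP 7.4 states a rule that sends them to imputation, and no visible section scores them. The primary ITT estimate then moves toward the FAS estimate. As a measure of device success, it is too high by at most about 0.75 to 2.25 points. That size rests on 2 to 6 implant failures in 200, 75% success in the others and a model without relevant predictors, all of which are assumptions.

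For retreated subjects, the verdict is limited to an unresolved conflict among SAP 2, 7.4 and 7.13.3.

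Two stronger inferences fail. First, the comparison with 50% is not undermined: it does not change near 75%, SAP 6 only examines the rate against that threshold, and Protocol 9.2 sets no success criteria. Second, the enrolment, screen-failure and ITT definitions also need reconciling (Protocol 4.3.3, 5.6, 6 and 9.3; SAP 2 and 5), but that is a separate matter of unknown size and does not add to this one. The item should be fixed because the change is small and the tilt favours the device.

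**What to change.** In SAP 7.4:
1. Score implant failures and subjects with a reported retreatment as primary effectiveness failures, without imputation.
2. Restrict multiple imputation to implanted, non-retreated subjects with no qualifying image.
3. State that this is a device-success (composite) estimand and that it was chosen. Occlusion regardless of the treatment given cannot be observed for implant failures, because their follow-up ends at discharge.
4. Keep the rule as now written as a labelled sensitivity analysis.
5. Reconcile SAP 2 with SAP 7.13.3 on who determines retreatment, and Protocol 21 with SAP 7.2.1 on what counts as retreatment.

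The cost is a few SAP sentences and a few lines of programming. The reported rate would be slightly less favourable, and it would understate occlusion if some implant failures are occluded by alternate treatment.
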